Quick Inventory of Depressive Symptomatology- Self Report (QIDS-SR) (Appendix): The QIDS-SR (Rush et al., 2003) is a self-report measure of depressive symptoms consisting of 16 scale items with responses ranging from 0 to 3, including one suicide item (item #12). Higher scores correspond with greater depression severity, and the measure is well-validated, sensitive measure of symptom severity in depression. The response choices on the suicide item include 0: "I do not think of suicide or death"; 1: "I feel that life is empty or wonder if it's worth living"; 2: I think of suicide or death several times a week for several minutes"; and 3: "I think of suicide or death several times a day in some detail, or I have made specific plans for suicide or have actually tried to take my life". The QIDS-SR will be used to determine eligibility at the baseline screening visit and to assess depressive symptoms at subsequent assessment visits.

Suicide item (Appendix): A question assessing the presence and nature of suicidal thoughts will be delivered weekly to participants via the app (or REDCap for those in the control condition) to monitor for risk concerns during the trial. Scores >0 will trigger a popup message to the participant about calling 988 or 911/going to the ER and will provide information about contacting a suicide hotline. Scores >1 will also trigger a text message alert to the clinician with the specific item response given by the participant (e.g., 2 vs. 3). The clinician will follow up with the participant within 24 hours by phone to assess for risk, and to refer to a higher level of care if clinically indicated (see Minimizing Risks, below).

Columbia-Suicide Severity Rating Scale (C-SSRS) (Appendix): The C-SSRS (Posner et al., 2010) is a gold-standard, clinician-administered assessment of suicidal ideation and suicide

behaviors. The baseline version, which assesses both lifetime and recent time frames, will be used to establish eligibility at the baseline/screening visit. The “Update” version, which assesses suicide risk since the last assessment, will be used at subsequent study administrations.

Assessment of Functioning and Quality of Life

Work and Social Adjustment Scale (Appendix): The WSAS is a self-report measure of impairment in occupational, social, and family domains (Mundt et al., 2002).

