Figure 1. Data flow and storage chart –Overview of All Data Sources.

See

Figures 2-14 in “Independent Monitoring of Source Data” for a detailed diagram and description of the data flow and storage described above in Figure 1. The administrative interface to this system will only be accessible to work stations on the PHS/MGH network. Of note, the CBT app architecture and code base were previously evaluated in #2017P000293, which is exactly equivalent to that described here. Similarly, the substantially equivalent REDCap and Beiwe flow and storage have been previously evaluated in #2017P000293 and #2019P002041 respectively.

Minimizing of Risks and Safety Reporting

The following procedures will be implemented to protect participants against risks. The information provided in this section pertains to all study phases, unless otherwise indicated.

1. Participants with active suicidal ideation at the screening assessment will be excluded from participating (see Inclusion/Exclusion Criteria). If a subject scores ≥ 21 on the

QIDS-SR and/or >1 on the self-report suicide questionnaire, the independent evaluator will follow up with a phone evaluation within 24 hours and refer the participant to a higher level of care if clinically indicated. Suicidal ideation at screening is also measured using the C-SSRS (see Inclusion/Exclusion criteria), and if a potential participant scores ≥ 2 , a study clinician, PI, or independent evaluator will conduct a risk evaluation with the participant and refer the participant to a higher level of care if clinically indicated.

2. Participants with severe major depressive disorder will be excluded from participating (see Inclusion/Exclusion criteria).
3. A disclaimer that is accessible from the home page of the digital CBT program and control condition website will be presented to remind participants that if they are experiencing suicidal thoughts, they should seek professional help or go to the emergency room right away. Links to 988, 911 and suicide hotline numbers will be provided along with this disclaimer.
4. A general resources page will be available on the app and website at all times to participants, which will include a suicide hotline number.

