5. Participants' clinical improvement or deterioration will be assessed weekly via a participant-rated CGI-OCD collected via the app in the app-based CBT group or REDCap surveys in the supportive attentional control condition. Participants may be withdrawn from the study if their clinical condition deteriorates substantially. Deterioration will be defined by a rating of 6 (much worse) or 7 (very much worse) on the patient -rated CGI during three consecutive, weekly assessments and (2) PI judgment that remaining in the study is not in the participant's best interest. Of note, three consecutive weekly ratings of 6 or 7 on the weekly, participant-rated CGI-OCD will also trigger a notification to the clinician via text message or email. In the case that a BA-level coach is notified that a participant's CGI indicates deterioration, they will notify a doctoral-level clinician as soon as possible (and within 24 hours). A study clinician will follow up with a phone evaluation within 24 hours of the alert and refer the participant to a higher level of care if clinically indicated.
6. Ratings on a one-item self-report suicide questionnaire will be carefully monitored weekly via the app in the app-based CBT group or REDCap surveys in the supportive attentional control condition; a score >0 at any assessment will trigger a pop up message to be presented to the patient within the mobile app reminding participants that if they are experiencing suicidal thoughts, they should seek professional help or go to the emergency room right away. Links to 988, 911, as well as a national suicide hotline, will be provided within this popup notification. A score >1 will also trigger notification to the clinician/coach via text message or email. In the case that a BA-level coach is notified that a participant reported a score >1 , they will notify a doctoral-level study clinician as soon as possible (and within 24 hours). A study clinician, PI, or independent evaluator will follow up with a phone evaluation within 24 hours of the alert and refer the participant to a higher level of care if clinically indicated. To be able to determine which participant triggered the alert (i.e., to link the de-identified trigger with the actual

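### The only stated QIDS-SR safety trigger is a total of 21 or more. No rule clearly acts on the scale's own suicide item, which matters mainly at the 3- and 12-month visits

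*Combined protocol and SAP*

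**What the plan says.** The safety section, VII.D Minimizing of Risks and Safety Reporting, states its own reach: "The information provided in this section pertains to all study phases, unless otherwise indicated". Item 1 attaches a safety action to a QIDS-SR score of 21 or more and adds a second threshold in the same sentence: "QIDS-SR and/or >1 on the self-report suicide questionnaire, the independent evaluator will follow up with a phone evaluation within 24 hours". Exclusion criterion f (III.A) uses the same cut-off and calls it a total score.

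Under Measures Descriptions, the QIDS-SR has 16 items, "including one suicide item (item #12". That item's four responses run from 0 to 3, and response 3 covers frequent detailed thoughts, specific plans or an attempt. The scale's purposes are stated as follows: "The QIDS-SR will be used to determine eligibility at the baseline screening visit and to assess depressive symptoms at subsequent assessment visits".

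Two other suicide measures are described:

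- **A separate suicide item**, given weekly "to monitor for risk concerns during the trial". For this item, "Scores >1 will also trigger a text message alert to the clinician with the specific item response given by the participant". Item 6 of VII.D repeats the rule ("A score >1 will also trigger notification to the clinician/coach via text message or email") and requires a phone evaluation within 24 hours of the alert.
- **The C-SSRS.** The baseline version establishes eligibility. The Update version, "which assesses suicide risk since the last assessment, will be used at subsequent study administrations".

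**The concern.** A participant can record a suicide plan or attempt on a study form, and unless the depression total is also high, no sentence clearly says who must act on it or how quickly. The plan already treats a score above 1 on the weekly item as needing a clinician alert and a call within 24 hours. It would be inconsistent for an equally serious answer on the QIDS-SR to carry no stated response.

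In the 12-week treatment period the weekly item would usually pick up the same disclosure. Follow-up is less secure, because it is unclear which other suicide measure, if any, is given at the 3- and 12-month visits. What is at stake is the safety of individual participants. No endpoint, error rate or sample size is affected.

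**Working it through.** The plan states no figure on this point to reproduce. The check is threshold arithmetic and a comparison of text with schedule.

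**1. Can the total stand in for the item?** Assume item 12 adds its own score to the total; the documents do not give the scoring rule.

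- Item 12 scored 3: the other items must supply 21 − 3 = 18 points.
- Item 12 scored 2: the other items must supply 21 − 2 = 19 points.
- Exclusion f removes totals of 21 or more, so the highest eligible entry total is 21 − 1 = 20. After entry, the trigger fires only at a total above any eligible starting value.

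A participant with item 12 at 3 and a total of 20 therefore does not meet the total-score rule.

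**2. Does the above-1 trigger in item 1 cover item 12?** Item 1 names a self-report suicide questionnaire. Item 6 uses that name for the one-item weekly form, and both Measures Descriptions and the Measures Chart list that form separately from the QIDS-SR. The literal reading therefore leaves item 12 out. Against that, item 1 is mostly about screening, and the chart does not mark the weekly form at baseline. The only self-report suicide rating marked there is item 12, so the authors may have meant to include it. The wording is ambiguous.

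**3. What is scheduled?** The chart marks the QIDS-SR at 4 visits after randomization: weeks 6 and 12, and 3 and 12 months. Two fall in the treatment period, leaving 4 − 2 = 2 in follow-up.

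| Measure | Follow-up visits marked |
|---|---|
| QIDS-SR | 2 of 2 |
| C-SSRS Update | 0 of 2 (marked only at baseline re-assessment) |
| Suicide item | 0 of 2 (marked only under Weekly) |

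**4. How far can the chart be trusted?** Its category labels are displaced in the extracted text. Several visit columns do agree with the prose: CSQ at weeks 6 and 12, the neurocognitive tasks at week 4 and end of treatment, and uMARS at end of treatment. The technologist interview does not agree: the chart puts it at 3 months and the prose at end of treatment. The patient-rated CGI-I has a Weekly mark and separate marks at week 12 and at 3 and 12 months, which suggests, without proving, that the Weekly column does not extend to those visits. The blank cells are useful evidence but not conclusive.

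**5. What does the prose say about follow-up?** The weekly item has no stated stop date, and VII.D applies to all phases unless otherwise indicated. The C-SSRS Update wording may mean later study visits, in which case text and chart disagree. It may instead mean later administrations of that scale, in which case they agree and the chart places none at follow-up. In the CBT arm the weekly item is delivered by the app, and app access is stated only through the initial 3-month follow-up (Treatment Format). The 12-month visit is therefore the least clearly covered.

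**6. What else could catch it?**

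- A research assistant inspects each form within 1–3 business days (IX.B) and chases missing ideation ratings. No action is stated for a positive answer, and that interval can exceed 24 hours.
- The Adverse Events Form, the Y-BOCS and the clinician CGI-I are marked at both follow-up visits.
- VII.D item 7 allows withdrawal on PI judgment, and item 18 provides a designated contact person.

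None of these is tied to the item 12 answer or to the 24-hour standard.

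**The case against.** The strongest reply is that the plan may already cover this. Item 1 joins its above-1 threshold to the QIDS-SR, item 12 is the only self-report suicide rating the chart marks at screening, and above 1 is a natural cut on a 0–3 item. The weekly item sits in a section that applies to all phases and is described as running for the trial, so it may continue into follow-up. Control participants answer it in REDCap, so app access does not matter for them. The end of coaching removes no required responder, because a study clinician, the PI or the evaluator makes the call. If the C-SSRS Update is given at later visits, a clinician asks about suicide directly. Exclusion e removes participants with a C-SSRS ideation score of 2 or more at entry, and crisis resources are posted on the app and website. Appendix forms and data-flow figures are not shown and could contain an item 12 alert.

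Most of this stands as a limit on the point. A reader might infer that no suicide measure is given at follow-up, or that text and chart plainly contradict each other on the C-SSRS. The documents support neither: the weekly item's end is unstated, and the C-SSRS wording has two fair readings.

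The reply does not supply a sentence that clearly names item 12, sets a threshold for it and requires a response. If the authors meant item 1 to include it, saying so carries out their own intention.

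**Conclusion.** The point holds as a patient-safety improvement that should be made. Across the visible text, the only QIDS-SR score with a stated safety action is a total of 21 or more, and no rule clearly acts on item 12. A response of 2 or 3 on that item with a total of 20 or less meets no clearly stated QIDS-SR action rule at either follow-up visit.

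The size in participants is unknown. The documents give no figure for how often item 12 would exceed 1 at a total of 20 or less, and none is estimated here. The practical gap is small during treatment, uncertain at 3 months and least clearly covered at 12 months.

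This rests on reading the questionnaire named in item 1 as the weekly form, on item 12 adding its own score to the total, and on there being no item 12 alert in material that is not shown. Confidence is medium.

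**What to change.** At every QIDS-SR administration, including 3 and 12 months, set a REDCap alert to a study clinician for item 12 above 1 or a total of 21 or more. Follow it with the existing phone evaluation within 24 hours of the alert, as item 6 already requires for the weekly item. Name item 12 explicitly in item 1 of VII.D so that the rule does not depend on what the suicide questionnaire is taken to mean.

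Two secondary clarifications: state when the weekly suicide item stops, and align the C-SSRS Update schedule between Measures Descriptions and the chart, saying whether it is given at weeks 6 and 12 and at 3 and 12 months.

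The cost is a wording change and one alert on a form already in use. The downside is some extra clinician calls, and clinician cover until the last 12-month form is in.

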Potential participants will be preliminarily screened by the RA, [name], or [name] over the phone to establish their likely eligibility. During the phone screen the RA may ask permission to send eligible and interested participants a Partners/MGH Authorization for Release of Protected or Privileged Health Information form, which participants may complete with their psychiatrist's or other healthcare provider's contact information and then send directly to the study RA. If permission is obtained, the study clinician may then contact the participant's healthcare provider to verify issues surrounding potential eligibility (e.g., if there is any question/concern about the anticipated stability of the participant's medication), based on information collected by the RA during the phone screen. All participants will be enrolled by MGH. Potential participants will be given as much time as they need to consider participation, prior to providing informed consent. If suicidality is expressed to an RA during the phone screen, the RA will notify a licensed clinician from the study staff immediately. Per our internal

procedures, RAs will keep the suicidal individual on the phone until a licensed study staff clinician is able to assess the individual.

Interested and eligible participants will be invited to complete the baseline assessment with the IE via any Partners-approved, secure, HIPAA-compliant clinical video platform, such as Enterprise Zoom or Virtual Visit, as recruitment is nation-wide. At that time, patients will be informed about the study's purpose and procedures and advised about alternative treatment options. Before eligibility is assessed, the IE, [name], [name], or [name] will obtain electronic informed consent. The informed consent document will be provided to the potential participant electronically through REDCap and they will be asked to select an "I agree" button and provide their signature in REDCap to indicate their consent (see more REDCap information below: "Privacy and Confidentiality" and "Monitoring and Quality Assurance"). The participant will be informed that they may download and save a copy of the consent form for their records. Self-report measures for the baseline assessment will be completed through a secure REDCap link emailed to participants if participants consent and are deemed eligible.

C. Procedures for obtaining informed consent (including timing of consent process)

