participants' name) and to be able to contact the person (i.e., to be able to look up that person's telephone number), the clinicians on call will require remote access to the key that links the de-identified study ID with the patient identifier. We will use Partners Dropbox Business to store this password-protected Excel spreadsheet that links the participants' de-identified and identified data. Partners Dropbox Business is a secure and appropriate platform for storing participant de-identified and identified data (see attached RISO approval). Access to this secure spreadsheet will only be provided to those who are directly responsible for risk assessment and will be provisioned/deprovisioned accordingly as clinicians join or depart the study.

7. Participants may also be withdrawn if, in the judgment of the PI, remaining in the study poses a substantial risk to the participant or a higher level of care is needed.
8. Treatment through app-based CBT or HealthWatch will be supplemented with communication with a study coach, who can answer questions and guide participants through the treatment as needed. Study coaches will be trained BA-level research assistants who will supervised weekly by licensed, doctoral level clinicians who are experts in OCD and related disorders. See *In-App Coach Training and Qualifications*, above, for details.
9. The independent evaluator(s) will be highly experienced, highly trained, and closely supervised.
10. [name] will be available, if necessary, to discuss the study, alternative treatments, or any concerns about the study with participants if requested by the participant, coach or rater.
11. Drs. [name], [name], [name], and the participants' study clinician/coach will be available to answer study questions via the app or phone. This will be clearly communicated orally and in writing to study participants.
12. All participants will be provided with referral resources.
13. The study clinicians, coaches, and raters will make every attempt to help participants feel comfortable when discussing sensitive material. Participants may skip questions on assessments that they are uncomfortable answering.
14. If exposure exercises suggested through the CBT app are too anxiety provoking, participants will be able to do alternative exercises that cause less anxiety.

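### In safety item 6 a coach may take as long to relay a suicide-item alert (24 hours) as the clinician has to make the call, and the recipient is looser than in the measure's own description

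*Combined protocol and SAP*

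**What the plan says.** The rules are in section VII.D of the combined protocol and SAP, under Minimizing of Risks and Safety Reporting.

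**Item 6 (weekly suicide item).** A score above 1 "will also trigger notification to the clinician/coach via text message or email". When the person notified is a bachelor's-level coach, "they will notify a doctoral-level study clinician as soon as possible (and within 24 hours". The staff response is then: "A study clinician, PI, or independent evaluator will follow up with a phone evaluation within 24 hours of the alert". The continuation of item 6 adds that on-call clinicians need remote access to the file linking study ID to name, so that they can identify and reach the participant.

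**Suicide item, Measures Descriptions.** The same weekly question, in both arms and at the same threshold, sends a text message to the clinician, who phones within 24 hours.

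**Item 5 (three consecutive poor weekly CGI ratings).** The trigger "will also trigger a notification to the clinician via text message or email". A coach who is told has the same outer limit as in item 6, "they will notify a doctoral-level clinician as soon as possible (and within 24 hours", and the call has the same deadline: "A study clinician will follow up with a phone evaluation within 24 hours of the alert".

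**Phone screen, section IV.A.** If suicidality is expressed to a research assistant, "the RA will notify a licensed clinician from the study staff immediately". Item 8 says of the coaches: "Study coaches will be trained BA-level research assistants".

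**The concern.** The telephone evaluation is the staff response that the protocol commits to when an enrolled participant scores above 1 on the suicide item. For that commitment to be safe when the alert reaches a coach first, the relay has to use up only part of the time allowed for the call. Item 6 lets it use all of it. A coach could stay within the stated relay limit and still hand the case over when the call is already due.

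Item 6 also leaves the recipient open. It names clinician and coach together with a slash and does not say whether both or either receives the message. It then gives the coach a duty to inform a clinician, a duty that matters most when the coach hears first or alone. Section VII.C, on device malfunctions, likewise names coach and clinician together as recipients of weekly questionnaire responses. Staff who configure alerts from item 6 alone could set up a coach-only route without breaching its text. Staff who work from the Measures Descriptions could not.

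What is at stake is the timeliness of a safety contact. The pop-up with emergency and hotline links is a separate safeguard and does not replace the call.

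**Working it through.** No statistical formula applies. The check is a subtraction of stated time limits and a side-by-side reading of the sections.

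**Inputs**
- Coach relay limit, item 6: as soon as possible, at most 24 h.
- Call deadline, item 6: 24 h from the alert.
- Call deadline, Suicide item description: 24 h, with the clinician alerted directly by text.

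**Step 1: time left for the call when a coach is the first or only recipient.** Count both limits from the automated alert. Time left = call deadline − relay time.
- Relay at the permitted limit: 24 − 24 = 0 h.
- Immediate relay (about 0 h): 24 − 0 = about 24 h.

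**Step 2: time left when the clinician is alerted directly.** The relay time drops out and the full 24 h remains. This is the case in the Suicide item description, and in item 5 for CGI deterioration.

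**Step 3: which event starts the clock.** Item 6 does not define the alert. Its continuation speaks of a participant triggering the alert, which favours the automated message; Step 1 uses that reading. If the alert were instead taken to be the coach's message to the clinician (an assumption), the longest permitted interval from the participant's answer to the call would be 24 + 24 = 48 h.

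**Step 4: the relevant rules side by side.**

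| Place | Who is alerted or told | Channel | Limit on relay by junior staff |
|---|---|---|---|
| Item 6, score above 1 | Clinician/coach, both or either not stated | Text or email | 24 h at most |
| Suicide item, Measures Descriptions, score above 1 | Clinician | Text | None needed |
| Item 5, CGI deterioration | Clinician | Text or email | 24 h at most, as a second route |
| Phone screen, section IV.A | Research assistant tells a licensed clinician | Not stated | Immediate |

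The first two rows describe the same event and differ on recipient and channel. Of the four, only item 6 combines a possible coach-only route with a relay limit as long as the call deadline.

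**What cannot be computed.** The documents give no frequency for scores above 1, for alerts that reach only a coach, or for late relays. Nothing beyond the worst-case interval can be derived.

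**The case against.** The strongest reply is that the plan, read as a whole, already alerts the clinician directly. The Suicide item description says so for the same item, threshold and both arms. The continuation of item 6 has on-call clinicians identifying and contacting participants, and restricts the linking file to those directly responsible for risk assessment. No section makes a coach the sole recipient. This stands. A reader might infer from item 6 that the trial has no direct clinician alert for elevated suicide scores; the documents do not support that. What survives is that item 6, in the section that sets the safety procedures, is worded more loosely than the measure's description.

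A second reply is that the two 24-hour limits do not conflict. The coach must first act as soon as possible, and the call deadline binds whenever the relay comes. This also stands. A reader might call the limits contradictory, but both can be met. The zero-hour case needs a coach-only alert together with a relay at the last permitted moment. It remains true that the outer limit, as a limit, gives the call no protection.

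Third, a reader might extend the point to item 5, which pairs the same two limits. There the notification goes to the clinician, so the coach's relay is a second route and the full 24 hours remain. The worst case does not carry over.

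Fourth, the phone-screen rule concerns a person live on the line, whom the research assistant keeps there until a clinician can assess them. It is not a ready-made standard for an automated alert. The comparison shows only that the protocol already uses an immediate relay for suicide risk, by staff of a similar kind.

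Finally, other safeguards exist: the pop-up at any score above 0, a designated relative or friend, and exclusion of active suicidal ideation at entry. They lower the severity of the point without removing it.

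**Conclusion.** The point holds for item 6 as a minor, cheap improvement to participant safety. The coach's outer relay limit equals the call deadline, so a relay at that limit leaves 0 of 24 hours for the call when a coach is the first or only recipient. Separately, item 6 is looser on recipient and channel than the description of the same measure. The conclusion rests on two assumptions: that the alert means the automated message, and that item 6's wording permits a coach-only notification, which it does not exclude but which other sections make unlikely. The size is a worst-case interval, not an expected delay. No endpoint, sample size or analysis is affected.

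**What to change.** In item 6:

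1. Align the recipient with the Suicide item description, so that every score above 1 alerts the on-call study clinician directly, with the coach only as an additional recipient.
2. Replace the coach's 24-hour relay limit with an immediate relay, the standard already used at the phone screen.
3. Keep the 24-hour call deadline and state that it runs from the automated alert.

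Item 5 already alerts the clinician directly, so shortening its relay limit is optional.

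The cost is a protocol wording change, alert-recipient settings in the app and in REDCap, and a short instruction to coaches. On-call clinicians may receive slightly more alerts. Visits and assessments stay as they are.
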